TITLE: Evaluation of two different methods of teaching self-management strategies to patients with symptomatic knee osteoarthritis

NCT: 03245463

DOCUMENT DATE: July 25, 2017

**Title:** Evaluation of two different methods of teaching self-management strategies to patients with symptomatic knee osteoarthritis

**Principal Investigator:** [name], MD

**Condition or Intervention to be studied:** The condition being studied is self-management education for patients who have symptomatic knee osteoarthritis (OA) and are scheduled for a hyaluronic acid (HA) injection.

**Research questions/specific aims:** This is a pilot study to evaluate two different teaching methods of self-management education to patients receiving an HA injection for symptomatic knee OA. The main goal is to see if the study can be feasibly conducted. Feasibility will be determined by availability of the fellows/residents to administer the assigned teaching method to the potential patient (if they are unavailable 70% of the time, then the study will be deemed to be not feasible). The other goals are to obtain information on the following:

1. Patient satisfaction with their assigned teaching methods.
2. Education methods that are preferred by patients.
3. Provider (fellows and residents) satisfaction with their assigned teaching methods.
4. Teaching methods that are preferred by fellows and residents.

**Hypothesis:** We hypothesize that the study can be feasibly conducted, and that patient satisfaction with assigned teaching method 2 (education handout + 5-minute explanation) will be higher than patient satisfaction with assigned teaching method A (educational handout only, no explanation).

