**Secondary outcomes:**

1. Patient preference regarding teaching method – assessed at 1 and 3 months post-injection
2. Provider preference regarding teaching method – assessed at 1 month post-injection
3. Quality of education on post-injection care – assessed at 1 and 3 months post-injection
4. PROMIS-10 – assessed at 1 and 3 months post-injection

**Background:** Symptomatic knee OA is a condition that is characterized by frequent pain to the joint and affects approximately 10 million adults in the United States. By age 60, the lifetime risk of being diagnosed with symptomatic knee OA is 9.29%. Increases in symptomatic knee OA pain have been associated with higher BMI, greater comorbidity, and lower level of education. For patients who do not want to have surgery, treatment options include pharmacologic injections, physical therapy, and medications, with the goal of relieving symptoms, improving quality of life, and restoring physical function. Regardless of treatment type, achieving the abovementioned goals requires self-management.

In 2003, the EULAR consensus stated that patient education should be provided to patients with symptomatic knee OA to help them understand and self-manage their condition.

However, there is a lack of consensus on the best teaching methods to educate our patients with symptomatic knee OA on self-management strategies. Different physician practices within a department or across different departments utilize different strategies to accomplish these goals. Many provide direct doctor-to-patient teaching that may occur during an office visit (one-on-one) or with a small group. Others may rely on educational handouts or other forms of individual education that are given to patients. Some utilize both methods of teaching, and others rely on physical therapists to provide this education to their patients as part of their physical therapy program. There are many other teaching methods, and variations of previous methods also exist.

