**Exclusion criteria:**

1. Patients who are already enrolled in the study
2. Non-English speaking

**Study procedures:** Patients who have symptomatic knee OA and are coming in for an HA injection will be approached for the study. At the time of consent, patients will be told that they will be receiving educational materials, and that the study will be focusing on outcomes in patients who receive educational materials. Details related to the two teaching methods will only be revealed to the patients at the 3-month follow-up, in order to prevent any bias in their responses. The primary investigator and research assistant will be blinded to the randomization group.

Enrolled patients will be randomized to receive one of two teaching methods:

1. A written handout will be given to the patient, and the patient will be asked to read the handout at home and call back with any questions or clarifications.
2. A written handout will be given to the patient, and key information will be explained to the patient with time for questions and answers (approximately 5 min).

The written handout includes a description of knee OA, treatment options for knee OA, and instructions for the self-management of knee OA.

During the icing period post-injection, a fellow or resident will return to the exam room and administer either teaching method 1 or 2 to the patient (depending on the randomization assignment). The same written handout will be given to every patient. The explanation of key information will be standardized as much as possible to prevent against large variations in teaching methods among fellows and residents.

At 1 month following the educational handout/session, the fellows and residents will be surveyed regarding their satisfaction with the teaching method and if they would have preferred to teach the information in a different manner.

At 1 month and 3 months following the educational handout/sessions, patients will be asked the following questions:

1. On a scale of 0-10, with 0=not satisfied and 10=most satisfied, please rate your satisfaction with the education you received on the day of your injection.
2. Would you have preferred a different method of receiving education? If yes, what method?
3. Did the education you received help with the care of your osteoarthritis? If yes, please explain how it helped.
4. PROMIS-10 questionnaire (also administered at baseline, after consent)

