**Sample size analysis and statistical analysis plan:** As recommended by Julius, this pilot study will have a sample size of 12 per group (24 total). If deemed feasible, results from this study will be used to design larger, future studies.

Descriptive statistics will be employed for this pilot study. Patient/provider satisfaction results will be summarized as mean with standard deviation or median with 1st and 3rd quartiles. Patient/provider preference results (yes/no) will be presented as counts and percentages. Whether the education helped with the patient's care of OA (yes/no) will also be presented as counts and percentages. PROMIS-10 scores will be summarized as mean with standard deviation or median with 1st and 3rd quartiles. Comparisons between continuous or categorical variables will be assessed using the Student's t-test or Chi-square test, respectively.

1. Julius SA. Sample size of 12 per group rule of thumb for a pilot study. *Pharmaceut Statist.* 2005 Oct;4(4):287-291.

12. Lawrence RC, et al. Estimates of the prevalence of arthritis and other rheumatic conditions in the United States, part II. *Arthritis Rheum*. 2008 Jan;58(1):26-35.

13.

14. Losina E, et al. Lifetime risk and age of diagnosis of symptomatic knee osteoarthritis in the US. *Arthritis Care Res.* 2013 May;65(5).
3. Bastick AN, et al. Defining knee pain trajectories in early symptomatic knee osteoarthritis in primary care: 5-year results from a nationwide prospective cohort study (CHECK). *Br J Gen Pract.* 2016 Jan;66(642):e32-9.
4. Jordan KM, et al. EULAR Recommendations 2003: an evidence-based approach to the management of knee osteoarthritis: report of a task force of the standing committee for international clinical studies including therapeutic trials (ESCISIT). *Ann Rheum Dis.* 2003 Dec;62(12):1145-55.
5. Schrieber L, et al. Patient education. *Best Prac Res Clin Rheum.* 2004;18(4):465-476.
6. Friedman AJ, et al. Effective teaching strategies and methods of delivery for patient education: a systematic review and practice guideline recommendations. *J Cancer Educ.* 2011 Mar;26(1):12-21.
7. Koehn CL, et al. Patient education and self-management of musculoskeletal diseases. *Best Prac Res Clin Rheum.* 2008;22(3):395-405.

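### Baseline PROMIS-10 is collected but has no stated role in the arm comparison; adjusting for it would usually be more precise, at small cost

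*Combined protocol and SAP*

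**What the plan says.** Study procedures, patient question 4, lists the instrument among the 1- and 3-month questions and adds that it is taken beforehand: "PROMIS-10 questionnaire (also administered at baseline, after consent". Secondary outcomes, item 4, defines the outcome by the follow-up visits only: "PROMIS-10 – assessed at 1 and 3 months post-injection".

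The section on sample size and statistical analysis has two sentences that bear on it. The first is descriptive: "PROMIS-10 scores will be summarized as mean with standard deviation or median" (or quartiles). The second is the only comparison rule for any outcome: "Comparisons between continuous or categorical variables will be assessed using the Student's t-test or Chi-square test, respectively". Neither copy of this section in the combined document mentions change from baseline, a covariate or an adjusted estimate. The section also states that "results from this study will be used to design larger, future studies", if the pilot proves feasible.

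**The concern.** The trial records a pre-treatment value of an outcome and then does not say what it is for. The t-test sentence can be applied to the follow-up scores or to the changes from baseline. Both are unbiased over all randomizations, but their precision differs, and which is better depends on the baseline-to-follow-up correlation r. Follow-up scores are more precise if r is below 0.5, change scores if it is above. The documents give no value for r, so the plan cannot choose between them on its own information. Leaving the choice open also allows it to be made after the data are seen.

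ANCOVA with baseline as a covariate estimates the slope from the data, so r need not be guessed. It also yields the residual SD, which a larger trial would need if it adjusts for baseline PROMIS-10.

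The stakes are limited. Research questions/specific aims puts feasibility first ("The main goal is to see if the study can be feasibly conducted"), and neither the feasibility criterion nor the sample size depends on PROMIS-10. The satisfaction outcomes have no baseline measurement, so the point does not extend to them.

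**Working it through.** **Inputs from the documents.** 12 per group; 2 × 12 = 24, which matches the stated total. This figure is a pilot rule of thumb, so there is no power, effect size or SD to reproduce. Teaching is given after the injection, so a baseline taken after consent is a proper pre-treatment covariate, provided it is completed before the teaching, as the word baseline implies.

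**Assumptions, not in the documents.** Two-sided 95% intervals, normal data, equal SD (set to 1) at baseline and follow-up, all 24 analysed, and r varied from 0 to 0.8.

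**Half-width of the 95% interval for the arm difference, n = 12 per arm:**

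- Follow-up t-test: t(0.975, 22) × √(2/12) = 2.074 × 0.408 = 0.85, whatever r is.
- Change-score t-test: 2.074 × √[(2/12) × 2(1 − r)].
- ANCOVA: t(0.975, 21) × √[(2/12) × (1 − r²) × (1 + 1/20)], with t = 2.080. The factor 1 + 1/(2n − 4) = 1.05 is the expected cost of chance baseline imbalance when the slope is estimated.

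| r | Follow-up t-test | Change-score t-test | ANCOVA | ANCOVA ÷ follow-up |
|---|---|---|---|---|
| 0 | 0.85 | 1.20 | 0.87 | 1.03 |
| 0.2 | 0.85 | 1.07 | 0.85 | 1.01 |
| 0.4 | 0.85 | 0.93 | 0.80 | 0.94 |
| 0.6 | 0.85 | 0.76 | 0.70 | 0.82 |
| 0.8 | 0.85 | 0.54 | 0.52 | 0.62 |

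**The two t-tests against each other.** The width ratio, change to follow-up, is √[2(1 − r)]. That is 1.41 at r = 0 (41% wider), 1 at r = 0.5, and 0.63 at r = 0.8 (37% narrower).

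**Break-even for ANCOVA.**

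- Against the follow-up t-test, on standard error: (1 − r²) × 1.05 = 1, so r = √(1 − 1/1.05) = 0.22. Allowing for the lost degree of freedom, the half-widths are equal at r = 0.23.
- Worst case, r = 0: the standard error is √1.05 = 1.025 times as large, and the interval 1.028 times as wide.
- Against the change-score t-test, on half-width: (1 + r) × 1.05 × (2.080/2.074)² = 2, so r = 0.89. Above that, ANCOVA loses less than 0.005 SD.

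**Simulation.** With no true effect and 100,000 trials at each r in the table, type I error was 4.8% to 5.1% for both the follow-up t-test and ANCOVA. The empirical SD of the ANCOVA estimate was 0.418, 0.411, 0.384, 0.335 and 0.252 as r rose from 0 to 0.8, against 0.408 to 0.409 for the t-test. A separate simulation of the variance ratios agreed with the formulas.

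**Fewer analysed patients.** With 8 per arm the inflation factor is 1 + 1/12 = 1.083. The break-even against the follow-up t-test rises to r = 0.28 (standard error) or 0.30 (half-width), and the worst-case interval is 4.8% wider.

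**How well the pilot can estimate r.** For an observed r of 0.6 in 24 patients, Fisher's transform gives 0.693 ± 1.96/√21 = 0.693 ± 0.428, which is 0.26 to 0.81 on the r scale. The factor 1 − r² then lies between 0.93 and 0.35.

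**The case against.** The strongest reply is that there is little real ambiguity. The outcome is defined at 1 and 3 months, the analysis section speaks of scores, and change from baseline is never mentioned. A t-test on follow-up scores is the likelier reading. I accept that. On that reading the baseline is simply unused in the comparison, and the gain of ANCOVA over the fixed 0.85 SD remains.

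Second, this is a pilot for which "Descriptive statistics will be employed for this pilot study"; no precision target is promised and no decision turns on PROMIS-10. That is true and is why the point ranks low. But the plan goes on to specify a between-arm test, and a test that is specified should make sensible use of data already collected.

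Third, r is assumed. Every patient also receives an injection before follow-up, so a correlation from untreated patients could not simply be carried over, and dropout raises the break-even. This stands as a limit on the size of the gain: that r will exceed 0.23 is plausible but cannot be shown from the documents. It does not alter the small worst-case loss.

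Fourth, the residual SD and r can be calculated later from the same data whether or not ANCOVA is named. That is correct. The planning argument is therefore a reason to commit to reporting them, not a claim that information would be lost. It applies only if the larger study adjusts for baseline PROMIS-10, which the documents do not say.

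**Conclusion.** The concern holds as an optional improvement. The plan gives baseline PROMIS-10 no role, and ANCOVA is a better default than either form of the t-test. At 12 per arm it costs at most about 3% in interval width against follow-up scores. It narrows the interval by 1 − 0.82 = 18% at r = 0.6 and by 1 − 0.62 = 38% at r = 0.8. It also beats change scores up to r of about 0.89. These figures rest on assumed r, equal SDs, normality and complete data.

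There is no bias and no error in the sample size. Even at r = 0.6 the interval is ±0.70 SD, so the gain is a better estimate, not a conclusion about PROMIS-10.

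**What to change.** Add to the analysis section: PROMIS-10 at 1 month and at 3 months will each be compared between arms by ANCOVA with arm and baseline PROMIS-10 as terms, and the adjusted difference will be reported with its 95% confidence interval. A single repeated-measures model with baseline as a covariate would also serve, but the plan should name one of the two and not leave both open.

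For planning, add that the unadjusted SD, the residual SD and the baseline-to-follow-up correlation with its 95% interval will be reported. The interval matters because r will be imprecise in 24 patients.

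The cost is one or two sentences, one degree of freedom and about 5% variance inflation. Precision is slightly worse than with the follow-up t-test if r turns out below about 0.22. No new data or visits are required.

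### Does naming only a chi-square test for the patient yes/no outcomes, at 12 per group, leave the results open to the choice of version?

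*Combined protocol and SAP*

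**What the plan says.** The section Sample size analysis and statistical analysis plan, which appears twice with the same content on this point, states that "this pilot study will have a sample size of 12 per group (24 total". It describes the analysis as descriptive. For the binary items it says "Patient/provider preference results (yes/no) will be presented as counts and percentages" and "Whether the education helped with the patient's care of OA (yes/no) will also be presented as counts and percentages". It then adds one sentence on testing: "Comparisons between continuous or categorical variables will be assessed using the Student's t-test or Chi-square test, respectively".

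The two patient items come from Study procedures: "Would you have preferred a different method of receiving education" and "Did the education you received help with the care of your osteoarthritis". Both are asked at 1 and 3 months, which gives four between-group comparisons. The first corresponds to the listed secondary outcome "Patient preference regarding teaching method". The second is not listed under that name; the nearest secondary outcome is the one on quality of education.

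The plan gives no significance level, continuity correction, exact test, rule for small expected counts or interval for a difference in proportions.

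**The concern.** At 12 per group, the tests that go by the name chi-square, and the exact test often used in their place, can give clearly different p-values on the same data. With 3 of 12 v 8 of 12, the uncorrected test is below 0.05 and the corrected and exact tests are about 0.10. If the version is not fixed in advance, it could be chosen after the data are seen. Small expected counts are also likely, which is the usual warning against the large-sample test. Finally, the pilot is meant to inform larger studies. For that purpose the size and precision of a difference matter more than a p-value, and no interval is planned.

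**Working it through.** **Inputs.** 12 per group and the chi-square test come from the analysis section; the two yes/no items at two visits come from Study procedures. The plan gives no significance level and no expected yes rate, so I assume two-sided 5% and show yes rates from 20% to 50%. Rates above 50% mirror these by exchanging yes and no. Provider items are left out because the number of providers is not stated and their answers may be clustered.

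**The plan's own figure.** 2 × 12 = 24, which agrees with the enrollment target. It rests on a rule of thumb, so there is no power calculation to reproduce.

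**One table by hand: 3/12 v 8/12.** With cells a = 3, b = 9, c = 8, d = 4:

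- Pearson: N(ad − bc)² / (product of the four margins) = 24 × (12 − 72)² / (12 × 12 × 11 × 13) = 86,400 / 20,592 = 4.20, p = 0.041.
- Yates: 24 × (60 − 12)² / 20,592 = 55,296 / 20,592 = 2.69, p = 0.101.
- Fisher: p = 0.0995.

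**All tables.** There are 13 × 13 = 169 outcomes at 12 v 12. Pearson is below 0.05 in 76; Yates and Fisher are below 0.05 in the same 60. The verdict therefore depends on the version in 76 − 60 = 16 tables. These are the four splits below, their yes/no mirror images, and the same with the arms exchanged (4 × 2 × 2 = 16).

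| Split of 12 | Pearson | Yates | Fisher |
|---|---|---|---|
| 0 v 4 | 0.029 | 0.100 | 0.093 |
| 1 v 6 | 0.025 | 0.072 | 0.069 |
| 2 v 7 | 0.035 | 0.092 | 0.089 |
| 3 v 8 | 0.041 | 0.101 | 0.0995 |

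**True false-positive rate.** This is the sum of the binomial probabilities of the rejected tables at a common yes rate.

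| Yes rate | Pearson | Yates or Fisher | Verdict depends on version |
|---|---|---|---|
| 20% | 3.9% | 1.2% | 2.7% |
| 30% | 4.9% | 1.7% | 3.2% |
| 40% | 5.9% | 2.1% | 3.8% |
| 50% | 6.4% | 2.3% | 4.1% |

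The 50% row gives the maximum for each test. At its worst Pearson is 6.4 − 5 = 1.4 points above nominal; Fisher at its closest is 5 − 2.3 = 2.7 points below it.

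**Losses to follow-up (assumed).** At 12 v 10, Pearson is 5.8% to 6.1% for yes rates of 20% to 50%. At 10 v 10 its maximum is 4.2%, and at 10 v 9 it is 6.5%.

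**Small expected counts.** A smallest expected count below 5 occurs in 99%, 85%, 51% and 31% of samples at the four rates. These samples do not cause the excess: at a 40% rate, Pearson rejects in 5.7% of them and in 6.2% of the rest.

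**Cost of the alternatives.** For true rates of 25% v 67%, power is 60.8% with Pearson, 50.5% with Boschloo's exact test and 43.2% with Fisher.

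**Precision.** From the reported counts 3/12 and 8/12, a reader obtains a difference of 8/12 − 3/12 = 42 points, with a 95% Miettinen-Nurminen interval of 0.9 to 70.6 points.

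**The case for a change.** The strongest case for a change is that the paragraph calls the analysis descriptive and still commits to between-group tests. If tests are run, their version should be known beforehand. The corrected statistic is also called a chi-square test, so the words do not strictly settle the matter. The disagreement is largest when there is something to find: at true rates of 20% v 60%, Pearson rejects in 56.8% of samples and Fisher in 39.2%, so the verdict depends on the version in 17.6%. One sentence would settle it, and an interval would serve the design of the next study better than a p-value.

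Part of this stands: no version is named and no interval is planned. Neither omission does much harm. The p-value is not reported alone, because counts and percentages are promised for these items. With about 12 patients per arm, anyone can recompute every version or any interval from them, so a choice made after the fact would be visible.

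Nor is there a replacement that is clearly better. Fisher is further from the nominal level and loses power. Boschloo's test keeps its level (maximum 4.5% at 12 v 12) but is not a single test once the arms are unequal. For 3/12 v 7/10 it gives 0.058 if tables are ordered by the two-sided Fisher p-value, and 0.046 if the smaller one-sided p-value is doubled. Writing in that name alone would leave the same ambiguity after losses.

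**Conclusion.** No change is needed. The omission is one of detail that an analyst can fill sensibly by reading the named test as uncorrected Pearson. On that reading, the false-positive rate at 12 v 12 is 3.9% to 6.4% for yes rates of 20% to 50%, and at most 4.2% at 10 v 10. Moving to Fisher or Boschloo is a trade of power for level on which reasonable statisticians differ. With no true difference, the verdict depends on the version in 2.7% to 4.1% of samples per comparison; about 18% is reached only with a difference as large as 20% v 60%.

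Nothing in the study depends on these p-values. Feasibility is judged by the availability of fellows and residents (Research questions/specific aims), and the comparative hypothesis concerns satisfaction scores (Hypothesis). Labelling any such p-value exploratory and giving an interval beside the counts would be good reporting practice, and the plan as written allows it.

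The conclusion assumes a two-sided 5% level, independent patients, and the plain Pearson reading. It does not cover the provider yes/no items.

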**Primary outcome:**

1. Patient satisfaction with their assigned teaching method (0-10 scale; 0=not satisfied; 10=most satisfied) – assessed at 1 and 3 months post-injection
2. Provider (fellow, resident) satisfaction with their assigned teaching method (0-10 scale; 0=not satisfied; 10=most satisfied) – assessed at 1 and 3 months post-injection

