**Sample size analysis and statistical analysis plan:** As recommended by Julious (1), this pilot study will have a sample size of 12 per group (24 total). If deemed feasible, results from this study will be used to design larger, future studies.

Descriptive statistics will be employed for this pilot study. Patient/provider satisfaction results will be summarized as mean with standard deviation or median with 1st and 3rd quartiles.

Patient/provider preference results (yes/no) will be presented as counts and percentages. Whether the education helped with the patient's care of OA (yes/no) will also be presented as counts and percentages. PROMIS-10 scores will be summarized as mean with standard deviation or median with 1st and 3rd quartiles. Comparisons between continuous or categorical variables will be assessed using the Student's t-test or Chi-square test, respectively.

1. Julious SA. Sample size of 12 per group rule of thumb for a pilot study. *Pharmaceut Statist.* 2005 Oct;4(4):287-291.

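### The pooled Student's t-test for 0-10 patient satisfaction loses calibration if the arms differ in both SD and number of responders; Welch's test is a near-free replacement

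*Combined protocol and SAP*

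**What the plan says.** The section on sample size and statistical analysis appears twice in the document, and both copies give the same rule for tests: "Comparisons between continuous or categorical variables will be assessed using the Student's t-test or Chi-square test, respectively". No unequal-variance, rank-based or ordinal alternative is named.

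The outcome this matters for is listed first under Primary outcome: "Patient satisfaction with their assigned teaching method (0-10 scale; 0=not satisfied; 10=most satisfied"), collected at 1 and 3 months. The Hypothesis is directional but gives no size: "patient satisfaction with assigned teaching method 2 (education handout + 5-minute explanation) will be higher than patient satisfaction with assigned teaching method A". Method A there is the handout-only arm, called method 1 in Study procedures.

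The summaries are more flexible than the test: "Patient/provider satisfaction results will be summarized as mean with standard deviation or median with 1st and 3rd quartiles". On numbers, "this pilot study will have a sample size of 12 per group (24 total"), justified by a pilot rule of thumb. The documents state no alpha, expected mean, SD, response rate or dropout allowance, and they plan no confidence interval for the between-arm difference.

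**The concern.** Student's t-test estimates one common variance for both arms. On a scale that stops at 10, an arm whose ratings move up towards the cap tends to have a smaller SD. So if the hypothesis is right and the scores are high, the equal-variance assumption may fail for the outcome the hypothesis concerns. The plan allows for skewed ratings in its summaries through the median and quartiles, but does not carry that over to the test.

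Unequal SDs do little harm when the arms are the same size. They matter when the analysed numbers also differ, and with follow-up at 1 and 3 months and no stated handling of non-response, equal numbers cannot be taken for granted. What is at stake is the precision attached to the satisfaction difference, which the plan says will feed the design of larger studies.

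**Working it through.** **The plan's own figure.** 2 × 12 = 24 agrees with the enrolment target. No alpha, power, effect or SD is given, so nothing further can be reproduced.

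**Inputs.** From the documents: the 0-10 scale, 12 per arm, Student's t-test. Assumed, because the documents are silent: means 6.9 (method 1) and 8.9 (method 2); method 1 SD 2.3; method 2 SD 1.57 or 1.0; responders from 12 down to 8 in one arm; two-sided 0.05.

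**Where the two method 2 SDs come from.** A normal distribution rounded to integers and capped at 0 and 10 reproduces mean 6.9, SD 2.3 with a latent SD of about 2.56. Shifting it upwards, with the latent SD unchanged, until the mean is 8.9 gives an observed SD of about 1.57. That is what the cap alone does. An SD of 1.0 at mean 8.9 needs a latent SD of about 1.14, so it also assumes that method 2 ratings are intrinsically less variable.

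**Standard errors.** With n1, s1 for method 1 and n2, s2 for method 2:

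- True variance of the difference: s1²/n1 + s2²/n2.
- Expected pooled variance: [(n1−1)s1² + (n2−1)s2²]/(n1+n2−2) × (1/n1 + 1/n2).

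At 8 v 12:

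- Cap alone: true 5.29/8 + 2.465/12 = 0.867. Pooled (7 × 5.29 + 11 × 2.465)/18 × 0.2083 = 0.742. SE ratio √(0.742/0.867) = 0.93.
- SD 1.0: true 5.29/8 + 1/12 = 0.745. Pooled (7 × 5.29 + 11 × 1)/18 × 0.2083 = 0.556. SE ratio √(0.556/0.745) = 0.86.

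At 12 v 8, with the narrower arm now the smaller, the SD 1.0 case gives true 5.29/12 + 1/8 = 0.566, pooled (11 × 5.29 + 7 × 1)/18 × 0.2083 = 0.755, and SE ratio 1.15. At 12 v 12 the two variances are identical and the ratio is exactly 1.

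**Coverage of a nominal 95% interval** (simulated capped integer ratings, Student v Welch):

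| Responders, method 1 v method 2 | Cap alone (SD 1.57) | SD 1.0 |
|---|---|---|
| 12 v 12 | 94.8% v 95.1% | 94.2% v 94.7% |
| 9 v 12 | 93.4% v 94.8% | 91.5% v 94.4% |
| 8 v 12 | 92.6% v 94.7% | 90.3% v 94.3% |
| 12 v 8 | not tabulated | 96.7% v 94.9% |

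A neighbouring ceiling model (means 7 v 9, SDs 2.25 v 1.48) gives Student 92.6% at 8 v 12 and 96.5% at 12 v 8, with Welch at 94.8% and 95.4%.

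**No difference between methods.** When both arms have the same capped distribution (both means 7, or both 9), Student rejects in 4.3% to 5.0% of trials at every split examined, from 12 v 12 to 6 v 12 and 12 v 6.

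**Cost of Welch when variances are equal** (1 SD difference): power 65.0% v 64.6% at 12 v 12, a loss of 0.4 points; 54.6% v 53.2% at 8 v 12, a loss of 1.4 points.

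**The case against.** The strongest reply is that the fault barely exists in the study as designed. The plan is for 12 v 12, where pooling does no material harm. The main goal is feasibility, the plan says that "Descriptive statistics will be employed for this pilot study", and no decision rule depends on this p-value. All of that stands, and it keeps the point minor.

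Four stronger readings are tempting, and the documents do not support them:

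- *Unequal response alone spoils the test.* It does not. With equal SDs, Student's type I error is 0.049 to 0.051 at every split; both SDs and numbers must differ.
- *The test yields too many false positives when the methods are equally satisfying.* Normal data with equal means and a 2:1 SD ratio do give 8.7% rejection at 8 v 12. But under the ceiling mechanism the SDs differ because the means differ, and identical rating distributions show no excess.
- *The handout-only arm will respond less, so the test will over-claim.* Nothing in the documents says so. Study procedures withhold details of the two methods from patients until the 3-month follow-up and blind the investigator and research assistant, which works against arm-related differences in follow-up. The opposite imbalance makes Student conservative.
- *The plan's error bars are wrong.* It specifies no confidence interval, and its per-arm SDs and quartiles are unaffected by pooling. The problem reaches only the test and any interval built from the pooled standard error.

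Nearness to the ceiling is also an assumption: the Hypothesis says only that one score will be higher.

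**Conclusion.** The point holds as a conditional and minor one. If the arms differ in both SD and number of responders, the pooled standard error for the satisfaction difference is miscalibrated, in a direction set by which arm loses more. On the assumed means and SDs, 8 v 12 responders leave a nominal 95% Student interval about 2.4 percentage points short if only the cap acts (95 − 92.6) and about 5 short if method 2's SD is 1.0, against at most about 1 point for Welch. At 12 v 12 the shortfall is below 1 point in both cases. None of these inputs comes from the documents, so the figures show a plausible range and do not predict what this study will find.

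**What to change.** In both copies of the statistical analysis paragraph, replace Student's t-test with Welch's unequal-variance t-test, and add that its 95% confidence interval will be reported for the between-arm difference in patient satisfaction at each of 1 and 3 months.

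The cost is a short edit to one sentence in each copy plus one added interval per time point, with no change to data collection or sample size. If the variances turn out equal, the price is about 0.4 points of power at 12 v 12 and 1.4 points at 8 v 12.
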